### 5.2.3. Analyses for Continuous Data

For the continuous secondary endpoints in the DB phase, a mixed model for repeated measures (MMRM) will be applied. The repeated measures mixed model will contain fixed effects for treatment (tofacitinib and placebo), visit, treatment by visit interaction, baseline value, baseline value by visit interaction. The baseline value in the model will be either DB

baseline value or OL baseline value, depending on the definition of the endpoint (ie, change from DB baseline or change from OL baseline).

An unstructured covariance matrix will be assumed with a Kenward and Roger method for degrees of freedom approximation provided the model converges, otherwise an alternative covariance matrix, eg, heterogeneous compound symmetry (CSH) will be attempted. If it still does not converge, compound symmetry will be attempted. If none of the covariance structures is computationally feasible, other approaches may be considered.

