**Table 1. Summary of Major Changes in SAP Amendments**

SAP Version (Date)	Associated Protocol Amendment	Change	Rationale
		the primary analysis (Sections 5.1, 5.2.1 and Appendix 1)	and small expected number of events can cause a significant impact of the efficiency or power of stratified log-rank test.
		Updated analysis method for binary endpoints from CMH to normal approximation (Section 5.2.2 and Appendix 1)	For consistency with updated primary analysis method
		Removed age group from MMRM (Section 5.2.3 and Appendix 1)	For consistency with updated primary analysis method
		Extended the on-study censoring time and risk period to the upper limit of the DB Week 52 visit window post randomization through both studies A3921165 and A3921145 (Section 5.3.1.1 and Appendix 1)	To align with updated study design and to ensure interpretability of results under the treatment policy estimand
		Updated Supplementary Analysis 2 under treatment policy estimand to include data up to 52 weeks post randomization (Section 6.1.2.1 and Appendix 1)	To align with updated study design and to ensure interpretability of results under the treatment policy estimand
		Updated the estimation and sampling method for tipping point analysis under composite estimand from Bayesian to MLE (Section 6.1.2.2 and Appendix 5)	Based on simulation results in response to FDA feedback on the Statistical Analysis Plan (Version 2, 24 Feb 2022)

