## **2.2. Study Design**

This is a 2-phase randomized withdrawal study to evaluate efficacy, safety and tolerability, and pharmacokinetics of tofacitinib as a treatment for sJIA. The study will enroll approximately 100 subjects from 2 to <18 years of age with sJIA with active systemic features.

The study will target enrollment of at least 12 subjects in the following age groups: from 12 to <18 years, from 6 <12 years, and from 2 to <6 years.

The study will conclude when the requisite number of flares are achieved during the double-blind phase of the study as described in [Section 5.1 Hypotheses and Decision Rules](#).

Subjects will be enrolled into an open-label phase during which they will receive tofacitinib 5 mg twice daily (BID) oral tablets, or an equivalent weight-based lower dose of tofacitinib oral solution (1 mg/mL) BID for subjects <40 kg. The 5 mg BID dose level of tofacitinib will be evaluated in a staggered fashion (cohorts of 7 subjects followed by safety review).

The open-label phase will be divided into two parts. In Part 1, all subjects must achieve and maintain a protocol-defined minimum level of clinical response for at least 4 weeks. In Part 2 of the open-label phase, subjects treated with background CSs >0.2 mg/kg/day oral prednisone (or equivalent) will attempt to have their CS dose tapered to a predetermined target range, or lower; subjects who successfully taper their CS dose while maintaining the defined clinical response, will be eligible for the double-blind withdrawal phase of the study. The minimum total duration of treatment with a stable dose of tofacitinib for subjects completing Parts 1 and 2 must be 12 weeks to qualify to enter the randomized withdrawal phase of the study.

In the double-blind withdrawal phase, “responders” from Part 1 and Part 2 of the open-label phase will be randomized in a 1:1 ratio, stratified by age group (from 12 to <18 years, from 6 <12 years, and from 2 to <6 years), to either continue tofacitinib or withdraw from tofacitinib and start placebo. The primary endpoint of the study is time to sJIA flare in the double-blind phase. The double-blind withdrawal phase will continue until a sufficient number of flares are reported as described in Section 5.1.

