### 5.2.1. Analyses for Time-to-Event Data

Time-to-event endpoint, i.e., time-to-flare in the double-blind randomized withdrawal phase, will be summarized using the Kaplan-Meier method and estimated survival curves will be displayed graphically. The median and quartiles for the time to event and survival (event-free) probabilities at particular time points along with 95% confidence intervals (CIs) will be estimated. The 95% CIs for both the estimated probability of event and the probability differences between the treatment groups at the target day of each windowed visit ([Appendix 3.13](#)) will be generated using Greenwood's formula.

Details on the censoring of time-to-flare for the primary analysis can be found in [Section 6.1.1](#) and for supportive analyses can be found in [Section 6.1.2](#).

The unstratified log-rank test will be used to compare the time to event between the treatment groups.

Hazard ratios (tofacitinib/placebo) and 95% CIs will be obtained from a Cox Proportional hazards model with treatment group as covariate. Repeated confidence interval will also be provided to account for alpha spending, when appropriate. This will be done as a supportive analysis for the log-rank test comparison between the treatment groups.

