**Table 4. Summary of Efficacy Analyses**

Endpoint	Estimand and Analysis Type	Population	Data Inclusion and Rules for Handling Intercurrent Events and Missing Data	Analysis Model
	Estimand 2 Composite Strategy  Secondary analysis		remission status before discontinuation. Investigational product discontinuation for any other reason are treated as non-response for active disease.  Missing responses are treated as active disease.	
ACR 30/50/70 response and JIA ACR inactive disease by DB visit and by subgroups: age, body weight, geographic region, formulation, OL baseline oral corticosteroids use, DB baseline oral corticosteroid use, OL baseline MTX use, prior bDMARD experience	Secondary estimand  Estimand 2 Composite Strategy  Subset analysis	DBFAS	For investigational product discontinuation due to study end and end of study treatment after clinical remission, use last JIA ACR value before discontinuation. Investigational product discontinuation for any other reason are treated as non-response/active disease.  Missing responses are treated as non-response/active disease.	Normal approximation
JADAS-27 ESR scores change from DB baseline by DB visit	Estimand 7 Hypothetical Strategy  Secondary analysis	DBFAS	Only data collected On-investigational product are included.  Missing data are not imputed and handled using MMRM.	MMRM with terms treatment, visit, treatment*visit, DB baseline, DB baseline*visit
JADAS-27 CRP scores change from DB baseline by DB visit	Estimand 7 Hypothetical Strategy  Secondary analysis	DBFAS	Only data collected On-investigational product are included.  Missing data are not imputed and handled using MMRM.	MMRM with terms treatment, visit, treatment*visit, DB baseline, DB baseline*visit

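### Age group stratifies the randomisation but was removed from the double-blind MMRM for a reason that does not apply to it; restoring it costs 2 degrees of freedom

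*SAP*

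**What the plan says.** - **Randomisation.** SAP 2.2 has responders randomised 1:1, "stratified by age group (from 12 to <18 years, from 6 <12 years, and from 2 to <6 years"). Protocol 4.3 and 5.1 agree that age group is the stratification factor.
- **Continuous endpoints.** SAP 5.2.3 specifies one MMRM that "will contain fixed effects for treatment (tofacitinib and placebo), visit, treatment by visit interaction, baseline value, baseline value by visit interaction". The MMRM rows of SAP Table 4 repeat this, for example "MMRM with terms treatment, visit, treatment*visit, DB baseline, DB baseline*visit", or the same terms with the open-label baseline. None includes age.
- **How age left the MMRM.** The version 3 entries in SAP Table 1 include "Removed age group from MMRM (Section 5.2.3 and Appendix 1"). The reason given is consistency with the updated primary method, and no reason specific to the MMRM is added.
- **How age left the primary analysis.** A separate row of Table 1 makes the log-rank test unstratified and removes age from the Cox model. Its reason is small expected strata and few expected events, which may harm the efficiency or power of the stratified log-rank test. In the current SAP 5.2.1 the hazard ratio is "obtained from a Cox Proportional hazards model with treatment group as covariate", in support of the log-rank comparison.
- **Where age remains.** SAP 6.4 plans age subgroups for time to flare, occurrence of flare, ACR 30/50/70 and JIA ACR inactive disease. The MMRM endpoints are not among them.

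**The concern.** Stratified randomisation balances age between the arms, so age differences contribute little to the chance variation of the treatment contrast. An analysis gets the benefit only if age is in the model. Otherwise the variation due to age stays in the residual variance, and the reported standard error describes an unstratified trial.

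The sparse-strata argument concerns a test that compares children only within their own stratum, so that a stratum of a few children with hardly any flares contributes almost nothing. A main effect in a linear mixed model works differently: it estimates two extra coefficients, and every child still informs the treatment contrast.

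At stake is precision on the continuous secondary endpoints (core set variables, JADAS-27, CHAQ, CHQ) in a trial planned to randomise 54 children.

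**Working it through.** **1. The plan's own figure, and whether it depends on this choice.** For 28 then 37 flares, SAP Table 2 prints efficacy z-values of -1.973 and -2.586 and power 80.4%.

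- Alpha spent at 28/37 = 0.757 of the information, gamma = 4: 0.025 × (1 - e^(-4 × 0.757)) / (1 - e^(-4)) = 0.025 × 0.9515 / 0.9817 = 0.0242, so z = -1.973.
- With drift ln(0.36) × √events / 2, bivariate normal integration gives a final z of -2.586 and power of 80.4%.

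Both agree with the SAP. No model covariate enters, so changing the MMRM leaves them as they are.

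**2. Is the sparse-strata premise real?** Yes. At least 12 children are targeted per age group (SAP 2.2) and about 55% are expected to be randomised (Protocol 10.1): 12 × 0.55 = 6.6 in the smallest stratum, or about 3.3 per arm.

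**3. Does it bear on the MMRM?** Three age levels need 3 - 1 = 2 parameters. For an endpoint measured at all 13 four-weekly visits to Week 52, the planned unstructured covariance already needs 13 × 14 / 2 = 91. Parsimony does not explain leaving out two.

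**4. Size of the gain.** Let R² be the share of residual variance, after the baseline value, that age group explains. The ratio of standard errors with and without age is about √(1 - R²), and the equivalent number of children without age is 54 / (1 - R²). R² is an assumption.

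| R² | SE ratio | SE reduction | Equivalent to 54 children |
|---|---|---|---|
| 0 | 1.000 | none | 54 |
| 0.05 | 0.975 | 2.5% | 57 |
| 0.10 | 0.949 | 5% | 60 |
| 0.15 | 0.922 | 8% | 64 |

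**5. Check by simulation.** A one-visit ANCOVA stood in for the MMRM: 54 randomised in permuted blocks of 4 within strata of 7/7/40 or 18/18/18, two-sided 5% level, 6,000 runs, and a treatment effect giving about 80% power. Each cell shows without age → with age.

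| Strata | R² | Mean SE | Type I error | Power |
|---|---|---|---|---|
| 7/7/40 | 0 | 0.2371 → 0.2377 | 0.053 → 0.054 | 79.0% → 78.6% |
| 18/18/18 | 0 | 0.2372 → 0.2377 | 0.051 → 0.051 | 79.7% → 79.4% |
| 7/7/40 | 0.10 | 0.2371 → 0.2249 | 0.039 → 0.051 | 80.3% → 83.8% |
| 18/18/18 | 0.10 | 0.2378 → 0.2256 | 0.040 → 0.051 | 80.0% → 83.3% |
| 7/7/40 | 0.20 | 0.2377 → 0.2126 | 0.032 → 0.050 | 81.9% → 87.8% |
| 18/18/18 | 0.20 | 0.2375 → 0.2121 | 0.030 → 0.049 | 82.3% → 88.4% |

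At R² = 0.10 the SE falls by 1 - 0.2249/0.2371 = 5.1%, as the formula says. At R² = 0 the cost is 0.2377/0.2371 - 1 = 0.3%. Small strata do not remove the gain.

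**The case against.** **No evidence that age is prognostic.** The documents do not show that age predicts outcome once baseline value and baseline-by-visit are in the model. This stands, and it is why the gain is given as a range starting at zero. It does not favour leaving age out, because the cost at zero is negligible.

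**Consistency is a legitimate aim.** The binary comparisons in SAP 5.2.2 and the Weibull imputation model in Appendix 5 are also unadjusted, so an age-adjusted MMRM would differ from them. This stands as a presentational cost. However, the MMRM already differs, because it adjusts for baseline value and they do not.

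**The stronger reading about Cox.** A reader might infer that age was dropped from the Cox model on the same thin ground, with the same loss of precision. The documents do not support this, for three reasons.

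- The Cox removal sits in the row that cites small strata and few events, not in the row that cites consistency. Few events bear on any Cox covariate. In a simplified simulation of strata 7/7/40 at 28 flares and a hazard ratio of 0.36, with all children entering together, some stratum had two or fewer events in 27% of runs with no age effect, and in 71% with assumed stratum hazard ratios of 1/1.5/2.25. In the latter case about 6% of age-adjusted fits gave no finite age estimate. With equal strata the problem disappeared.
- √(1 - R²) is a linear-model result. In the same work, adding age to the Cox model raised the mean SE of the log hazard ratio by about 1 to 4%. Any gain in power comes from a conditional hazard ratio lying further from 1.
- The primary estimand in SAP 2.3.1 contrasts the arms as randomised, with no conditioning on age. The treatment-only Cox model is the direct counterpart of the unstratified log-rank test, so that pairing is defensible.

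**Conclusion.** The point holds for the MMRM, as a low-cost improvement to secondary analyses. The stratification factor is missing, and the reason given rests on an argument about a different kind of analysis. If age is prognostic beyond baseline, the planned standard errors are too large by an amount that inclusion would recover: about 2.5%, 5% or 8% for 5%, 10% or 15% of residual variance.

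A reader might go further and infer inflated type I error, a biased treatment difference or a threat to the primary conclusion. None of these follows. The error is on the conservative side (about 0.04 against a nominal 0.05 at R² = 0.10), the mean difference is unbiased, and the log-rank decision rule, boundaries and power do not involve the MMRM. Nor can it be said that sparse strata are a reason against the stratified log-rank test alone, since stratified Cox and CMH analyses are exposed to them too.

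The sizes rest on an assumed age effect, the planning figure of 54 randomised, and a one-visit stand-in for the repeated-measures model.

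**What to change.** - In SAP 5.2.3 and every MMRM row of Table 4, add age group at enrolment (three levels) as a fixed main effect, under both the treatment-policy and the hypothetical estimands. Settle this before unblinding. If the sponsor prefers to omit age, give a reason specific to the MMRM.
- Keep the unstratified log-rank test as primary and the treatment-only Cox hazard ratio as its supportive estimate.
- Optionally, report an age-adjusted Cox hazard ratio as a labelled sensitivity analysis. State that it is a conditional hazard ratio and may be unstable if a stratum has few flares.

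The cost is SAP wording, one model term and 2 degrees of freedom. No new data are needed, because age group is already recorded for randomisation and subgroups. The continuous analyses would then be age-adjusted while the binary ones are not, which one sentence in the SAP can explain.

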- If the value of the test-statistic at the First Analysis crosses the futility boundary ($z \geq -0.286$, 1-sided $p \geq 0.387$), the trial may be stopped for futility.
- Otherwise, the trial will continue as planned. The Final Analysis will be performed after flares have been reported in approximately 40 subjects.

The efficacy and futility boundaries will depend on the number of flares. For logistical and administrative reasons, the actual number of flares at the First Analysis and the Final Analysis might differ slightly from those that have been pre-specified here. In that case appropriate adjustments will be made to the efficacy and futility boundaries based on the gamma family spending functions. The actual boundary used for the First or the Final Analysis will be re-calculated from the specified spending function based on the actual number of flares achieved at the time of First or Final analysis. These boundaries will be calculated and finalized prior to the evaluation of comparative data. More details regarding the calculation of futility and efficacy boundaries will be provided in the SAP.

Applying a 1:1 allocation ratio to treatment groups and an Adapted JIA ACR response rate of approximately 55% at the end of the open-label phase, it is estimated that approximately 100 subjects would need to be enrolled in the open-label phase to randomize 54 subjects in the double-blind phase. As of November 2022, 23 subjects have been randomized during the accrual period of 225 weeks. Assuming a future accrual rate of 0.315 subjects per week, it is anticipated that it will take a total of 262 and 358 weeks to achieve the requisite number of flares for the First and Final Analyses, respectively.

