### **3.4. Baseline Variables**

This study will have a separate type of baseline for each of its two phases. The open-label baseline will be defined as the last value collected prior to day 1 of tofacitinib administration in this phase. For the analyses in the double-blind phase, baseline will refer to the values collected at the randomization visit – before the administration of the assigned treatment in this phase for all endpoints, unless noted otherwise. For Adapted JIA ACR responses the open-label baseline will be utilized as the reference point.

Selected analyses in the double-blind phase, such as changes in laboratory parameters and vital signs, will also refer to the open-label baseline as a separate analysis, in addition to using the double-blind baseline.

In the double-blind phase change from baseline in each sJIA ACR core variable will be calculated with respect to both the open-label and double-blind baseline.

Age groups for stratification will be based on the age at enrollment in the open-label phase of the study. The age groups are: 2 to <6 years, 6 to <12 years, and 12 to <18 years.

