## 5. GENERAL METHODOLOGY AND CONVENTIONS

### 5.1. Hypotheses and Decision Rules

The primary null hypothesis in this study is that there is no difference between the distributions of time to disease flare in the double-blind randomized withdrawal phase between tofacitinib and placebo. The alternative hypothesis is that, among the subjects that meet the randomization criteria, time to disease flare is increased in the subjects remaining on tofacitinib in the double-blind withdrawal phase versus placebo subjects.

The difference between the distributions of time to disease flare will be tested using an unstratified log-rank test ([Schoenfeld, 1987](#); [Shih, 1999](#); [Yang, 2012](#)).

There will be potentially 2 planned analyses. The First Analysis will be performed after 28 subjects have reported flare in the double-blind phase. Number of flares required for the 2 planned analyses will be counted according to the definition of having a flare in the primary estimand ([Section 2.3.1](#)). The purpose of the First Analysis is to allow early stopping of the study for efficacy or futility, and to assess safety of tofacitinib. The investigators, subjects, and sponsor study team will remain blinded to treatment assignment in the double-blind phase through the entire duration of the trial until final database release.

If the study does not end for efficacy or futility at the First Analysis, a total of 37 subjects with flares will be required for the Final Analysis to yield an overall power of 80% using a log-rank test to detect the treatment difference, assuming a 1-sided type-I error rate of 2.5% and a 64% improvement in median time to flare (i.e., a hazard ratio of 0.36 and a median time to flare of 236 days for placebo; assumptions based on a similar sJIA randomized withdrawal trial). The number of flares needed at the Final Analysis will be based upon the actual number of flares at the First Analysis (additional details are provided below and in [Appendix 2](#)).

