#### **6.2.1.3. Supplementary Analyses**

For aJIA ACR 30/50/70/90/100 response at each scheduled visit in the double-blind phase through Week 52, an additional analysis using the treatment policy estimand strategy ([Section 2.3.4](#)) will be performed. It will use the same methodology and summary as in [Section 6.2.1.1](#) but will also include data collected after the intercurrent events of investigational product discontinuation, ie, all data collected while On- and Off-investigational product until Week 52 will be used to derive the endpoints.

For all DB continuous secondary endpoints listed in [Section 3.2.1](#) (change from DB baseline in JADAS-27 ESR/CRP, change from both OL and DB baseline in each sJIA ACR core variable, change from DB baseline in CHQ responses and CHAQ discomfort index), an analysis using the hypothetical estimand strategy (Section 2.3.4) will be performed. It will use the same methodology and summary as in [Section 6.2.1.2](#) but only the on-treatment data ([Appendix 3.13](#)) will be used.

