**Table 4. Summary of Efficacy Analyses**

Endpoint	Estimand and Analysis Type	Population	Data Inclusion and Rules for Handling Intercurrent Events and Missing Data	Analysis Model
CHAQ - Discomfort Index responses change from DB baseline by DB visit	Estimand 7 Hypothetical Strategy  Secondary analysis	DBFAS	Only data collected On-investigational product are included.  Missing data are not imputed and handled using MMRM.	MMRM with terms treatment, visit, treatment*visit, DB baseline, DB baseline*visit
CHQ responses change from DB baseline by DB visit	Estimand 7 Hypothetical Strategy  Secondary analysis	DBFAS	Only data collected On-investigational product are included.  Missing data are On-investigational product not imputed and handled using MMRM.	MMRM with terms treatment, visit, treatment*visit, DB baseline, DB baseline*visit
sJIA ACR core set variables change from OL baseline by DB visit, including  • number of joints with active arthritis • number of joints with limited range of motion • physician global evaluation of disease activity • parent/legal guardian/subject evaluation of overall well-being (from the CHAQ) • ESR	Secondary estimand  Estimand 3 Treatment Policy Strategy  Secondary analysis	DBFAS	All data collected On- and Off-investigational product are included.  Missing data are not imputed and handled using MMRM.	MMRM with terms treatment, visit, treatment*visit, OL baseline, OL baseline*visit
	Estimand 7 Hypothetical Strategy  Supplementary analysis	DBFAS	Only data collected On-investigational product are included.  Missing data are not imputed and handled using MMRM.	MMRM with terms treatment, visit, treatment*visit, OL baseline, OL baseline*visit
CHAQ disability index change from OL baseline by DB visit	Estimand 7 Hypothetical Strategy  Secondary analysis	DBFAS	Only data collected On-investigational product are included.  Missing data are not imputed and handled using MMRM.	MMRM with terms treatment, visit, treatment*visit, OL baseline, OL baseline*visit

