**Table 4. Summary of Efficacy Analyses**

Endpoint	Estimand and Analysis Type	Population	Data Inclusion and Rules for Handling Intercurrent Events and Missing Data	Analysis Model
sJIA ACR core set variables change from DB baseline by DB visit 

• number of joints with active arthritis

• number of joints with limited range of motion

• physician global evaluation of disease activity

• parent/legal guardian/subject evaluation of overall well-being (from the CHAQ)

• CHAQ disability index

• ESR

	Estimand 7 Hypothetical Strategy  Secondary analysis	DBFAS	Only data collected On-investigational product are included.  Missing data are not imputed and handled using MMRM.	MMRM with terms treatment, visit, treatment*visit, DB baseline, DB baseline*visit
CHAQ disability index change from DB baseline by DB visit	Secondary estimand  Estimand 3 Treatment Policy Strategy  Secondary analysis	DBFAS	All data collected On- and Off-investigational product are included.  Missing data are not imputed and handled using MMRM.	MMRM with terms treatment, visit, treatment*visit, DB baseline, DB baseline*visit
Steroid taper success in OL Part 2	Summary	OLPT2	Only use observed data	N/A
Steroid reduction to $\leq 0.2$ mg/kg/day or 10 mg/day in OL Part 2	Summary	OLPT2	Only use observed data	N/A
Adapted JIA ACR responses by OL Part 1 / 2 visit	Summary	OLPT1 / OLPT2	Only use observed data	N/A
JADAS-27 inactive disease CRP by OL Part 1 / 2 visit	Summary	OLPT1 / OLPT2	Only use observed data	N/A

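### Optional improvement: add the randomisation-visit value, by visit, to the five treatment-policy core-variable models that adjust only for open-label baseline

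*SAP*

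**What the plan says.** SAP 5.2.3 sets the MMRM fixed effects as treatment, visit, treatment by visit, one baseline value and that baseline by visit. The baseline is either the DB "baseline value or OL baseline value, depending on the definition of the endpoint".

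SAP 2.3.2.2 and 6.2.1.2 make treatment policy (Estimand 3) the main strategy for the six core variables. SAP Table 1 records this as a version 5 change after FDA feedback. Five variables are analysed as change from OL baseline: active joints, limited-motion joints, physician global, well-being and ESR. Their Estimand 3 entry in Table 4 is "MMRM with terms treatment, visit, treatment*visit, OL baseline, OL baseline*visit".

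The sixth is listed as "CHAQ disability index change from DB baseline by DB visit", and its Estimand 3 model carries DB baseline and DB baseline by visit.

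For the other five, DB baseline enters only through Estimand 7. SAP 6.2.1.3 describes that analysis as using the same methodology "but only the on-treatment data". SAP 3.4 defines DB baseline as the randomisation-visit value, taken "before the administration of the assigned treatment in this phase for all endpoints", unless noted otherwise.

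**The concern.** The OL baseline describes the child at entry, before the open-label phase that Protocol 4.3 puts at 12 to 40 weeks. The randomised arms separate only from the randomisation visit. The value at that visit is the most recent pre-treatment measurement of the same outcome, and it is missing from five of the six main models. If it predicts later values beyond what OL baseline explains, leaving it out gives wider intervals than necessary.

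At stake are the by-visit confidence intervals and p-values through Week 52 for secondary endpoints, in a trial that plans 54 randomised children. The time-to-flare test and the decision rules in SAP 5.1 are not involved.

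**Working it through.** **Plan figures.** The documents state no SD, correlation or precision target for these endpoints, so there is no plan figure for precision to reproduce. The accrual and flare projection can be reproduced, and it shows how many children each visit would have.

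**Children per visit.** Inputs from Protocol 10.1.1: "As of November 2022, 23 subjects have been randomized during the accrual period of 225 weeks", then 0.315 per week up to 54. From SAP 5.1: placebo median 236 days, hazard ratio 0.36, and "The First Analysis will be performed after 28 subjects have reported flare in the double-blind phase". I assume uniform past accrual and exponential flare times.
- Check: this gives 20.1 flares at week 262 and 40.0 at week 358, the two times and flare counts in Protocol 10.1.1.
- At 28 flares (week 301): 23 + 0.315 × 76 = 46.9 randomised. Those randomised by week 249 (30.5) could reach Week 52. Of them, about 51% (the mean of 34% and 68% in the two arms) are flare-free, or 15.6.
- At 37 flares (week 340): 54 randomised and 22.0 flare-free at Week 52.
- Remission exits are not modelled and would lower these counts. Children followed after stopping product for reasons other than flare would raise them.

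**One visit.** Let r be the partial correlation of DB baseline with the later value, given OL baseline. With k baseline covariates, the variance of the adjusted difference is inflated by 1 + k/(n − k − 3). Going from k = 1 to k = 2:

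SE ratio = √(1 − r²) × √{[1 + 2/(n − 5)] / [1 + 1/(n − 4)]} = √(1 − r²) × √[(n − 4)/(n − 5)]

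Break-even is at r = 1/√(n − 4).

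| n | (n−4)/(n−5) | r = 0 | 0.3 | 0.5 | 0.7 | break-even r |
|---|---|---|---|---|---|---|
| 54 | 50/49 | 1.01 | 0.96 | 0.87 | 0.72 | 0.14 |
| 30 | 26/25 | 1.02 | 0.97 | 0.88 | 0.73 | 0.20 |
| 22 | 18/17 | 1.03 | 0.98 | 0.89 | 0.73 | 0.24 |
| 15 | 11/10 | 1.05 | 1.00 | 0.91 | 0.75 | 0.30 |

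**One common slope, or a slope per visit.** I simulated 600 trials of 54 children with visits at Weeks 4, 12, 24 and 52 and unstructured covariance, fitted by maximum likelihood. Entries are empirical SE ratios against OL baseline only, at Weeks 4/12/24/52. The first column is the assumed correlation of DB baseline with later values, from Week 4 to Week 52.

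| Correlation | Common slope, no dropout | By visit, no dropout | By visit, exit after flare |
|---|---|---|---|
| 0.50 throughout | 0.893/0.879/0.894/0.873 | 0.898/0.889/0.895/0.866 | 0.903/0.909/0.918/0.932 |
| 0.56 to 0.30 | 0.845/0.907/0.951/0.978 | 0.843/0.917/0.955/0.967 | 0.827/0.888/0.929/0.989 |
| 0.76 to 0.11 | 0.698/0.855/0.949/1.089 | 0.660/0.856/0.941/1.004 | 0.645/0.841/0.953/1.025 |
| 0.14 to 0.08 | 1.006/0.996/1.002/1.006 | 1.004/1.008/1.009/1.015 | 0.988/1.014/1.017/1.005 |

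With fast decay, a common slope raises the Week 52 SE by about 9%. The by-visit form brings this back to 1.00, or 1.03 with exit after flare.

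A common slope can also misstate its own precision. In a separate 13-visit simulation (47 randomised, compound symmetry, r fading from 0.5 to 0.17), its Week 52 model SE ratio was 0.964 while the empirical ratio was 1.020. Since 0.964/1.020 = 0.945, the reported SE would be about 5.5% too small if the OL-only SE is calibrated.

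**Parameters.** Visits every 4 weeks to Week 52 number 52/4 = 13. The planned model has 13 × 2 = 26 visit and treatment terms plus 13 OL baseline terms, 39 in all. The by-visit addition brings 13 more, giving 52.

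**Limits.** The four-visit simulation is smaller than the planned 13-visit model and does not use Kenward-Roger. Differences of about a percent should not be read closely.

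**The case against.** **Estimand 7 already covers this.** It fits DB baseline and DB baseline by visit for all six variables. With baseline by visit in a model, using change from OL, change from DB or the raw value as response gives the same treatment contrast. The two datasets also overlap heavily, because flare ends participation. This stands in part: a DB-adjusted contrast will be reported. But Estimand 7 excludes off-treatment data, and SAP version 5 made treatment policy the main estimand, so the main analysis still lacks the covariate.

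**The gain is not assured.** This stands. Its size depends on correlations that the documents do not give. Values clustered near zero in responders at randomisation could make the covariate uninformative, and withdrawal to placebo could make the correlation fade.

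**SAP version 3 deliberately simplified these models.** It removed age group for consistency with the revised primary method. That reason does not bear on a pre-dose value of the outcome itself.

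**A reader might infer bias.** Flare is judged against randomisation-day values (SAP Appendix 3.3), so dropout depends on a value the five models omit. In simulation with correlation 0.5 and exit after flare, Week 52 bias was −0.047 SD with OL baseline only and −0.007 with the by-visit term. In the fast-decay case the two were 0.023 and 0.021. That exit rule used a rise in one variable, whereas the trial's rule needs three of six variables or fever. The documents do not support a claim of bias.

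**Conclusion.** The plan is coherent and contains no error here. The five main treatment-policy models omit a valid covariate that is already collected and that the sixth core variable's model already uses. Adding it is an optional, low-priority improvement in precision for secondary endpoints.

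At n = 54 it lowers the single-visit SE by about 4% at r = 0.3 and about 13% at r = 0.5. The gain shrinks at later visits if the correlation decays, and there is a small loss where r is below break-even (0.14 at n = 54, 0.30 at n = 15). All of this rests on assumed correlations.

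Two stronger readings are tempting. One is that the primary result or its power is weakened. The documents do not support it, because SAP 5.1 rests only on the unstratified log-rank test of time to flare. The other is that a single main effect would do. It can lose precision late and understate the late SE, whereas a by-visit term follows the SAP's existing baseline form and largely avoids this.

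**What to change.** Before unblinding, amend SAP 5.2.3, 6.2.1.2 and Table 4:
- For the five Estimand 3 models, add DB baseline and DB baseline*visit.
- Keep change from OL baseline as response, OL baseline, OL baseline*visit, the estimand and the treatment contrast.
- State a fallback for non-convergence with both sets of interactions: OL baseline as a main effect with DB baseline*visit. Say whether it comes before or after the covariance fallbacks already listed.
- Leave age group out of the MMRM, and leave the log-rank test and Cox model unchanged.

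The cost is SAP wording and one parameter per visit per model, 13 in each. No new data are needed. Protocol section 10 requires a protocol amendment only for major changes to the primary endpoint or its analysis, so this change does not call for one. The statistical price is an SE larger by about 1% (n = 54) to 5% (n = 15) at a visit where the value is uninformative, and a somewhat higher risk of non-convergence.
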